5.3.6.2 Adverse event collection and reporting

AE Collection

[figure not shown]
The Investigator shall maintain and keep detailed records of all AEs in their patient files. The following must be collected and documented on the appropriate eCRF(s) by the Investigator:

- From signing the informed consent onwards through the Residual Effect Period (REP, 10 weeks after the last study drug administration), until individual patient's end of trial:
 - all AEs (serious and non-serious) and all AESIs.

However, if an individual patient discontinues trial medication prematurely but stays in the trial (i.e., if further visits including telephone visits or vital status assessments

are planned) from then on and until the individual patient's end of the trial the Investigator must report related SAEs and related AESIs.

- After the individual patient's end of trial:
 - the Investigator does not need to actively monitor the patient for AEs but should only report relevant SAEs and relevant AESIs of which the Investigator may become aware of.

The residual effect period (REP) is defined as 10 weeks after the last trial medication application. All AEs which occurred through the treatment phase and throughout the REP will be considered as on treatment. Events which occurred after the REP will be considered as post treatment events.

AE reporting to sponsor and timelines

The Investigator must report SAEs, AESIs, and non-serious AEs which are relevant for the reported SAE or AESI, on the BI SAE form via fax immediately (within 24 hours) to the sponsor's / sponsor's designee unique entry point (contact details will be provided in the ISF). The same timeline applies if follow-up information becomes available. In specific occasions, the Investigator could inform the sponsor / sponsor designee upfront via telephone. This does not replace the requirement to complete and fax the BI SAE form.

With receipt of any further information to these events, a follow-up SAE form has to be provided. For follow-up information the same rules and timeline apply as for initial information.

Information required

For each AE, the Investigator should provide the information requested on the appropriate eCRF pages and the BI SAE form. The Investigator should determine the causal relationship to the trial medication and any possible interactions between the investigational drugs.

The following should also be recorded as an (S)AE in the eCRF and SAE form (if applicable):

- Worsening of the underlying disease that cannot be explained with the natural fluctuation of disease severity or of other pre-existing conditions
- Changes in vital signs, ECG, physical examination and laboratory test results, if they are judged clinically relevant by the Investigator.
- If such abnormalities already pre-exist prior to trial inclusion they will be considered as Baseline conditions.

All (S)AEs, including those persisting after individual patient's end of trial, must be followed up until they have resolved, have been sufficiently characterized, or no further information can be obtained.

Pregnancy

In rare cases pregnancy may occur in a clinical trial. Once a patient has been enrolled into this clinical trial and has taken trial medication, the Investigator must report immediately (within 24 hours) a potential drug exposure during pregnancy to the sponsor's / sponsor designee unique entry point (contact details will be provided in the ISF). The Pregnancy Monitoring Form for Clinical Trials (Part A) should be used.

The outcome of the pregnancy associated with the drug exposure during pregnancy must be followed up and reported to the sponsor's/sponsor's designee unique entry point on the Pregnancy Monitoring Form for Clinical Trials (Part B).

The ISF will contain the Pregnancy Monitoring Form for Clinical Trials (Part A and B).

As pregnancy itself is not to be reported as an AE, in the absence of an accompanying SAE and/or AESI, only the Pregnancy Monitoring Form for Clinical Trials and not the SAE form is to be completed. If there is an SAE and/or AESI associated with the pregnancy an SAE form must be completed in addition.

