Abbreviations: ; AE=adverse event; anti-HBc=anti-hepatitis B core antibodies; anti-HCV=anti-hepatitis C antibodies; DLQI=Dermatology Life Quality Index; EoT=End of Treatment; IRT=Interactive Response Technology; HBsAg=hepatitis B surface antigen; HIV=human immunodeficiency virus; IGRA=interferon gamma-releasing assay; ; PASI=Psoriasis Area and Severity Index; PPD=purified protein derivative; SFU=Safety Follow-up; sPGA=Static Physician's Global Assessment of psoriasis; TB=tuberculosis.

1. Patients will have to visit the site for efficacy assessments and to provide samples for / safety. For other visits (Weeks 3, 5, 7, 9, 11, 13, 15, 17, 19, 21 and 23), patients are allowed to self-administer the drug at home (after training).
2. Patients who discontinue the trial early (also those not achieved PACI 50 at week 16) will, at discontinuation, have an End of Treatment (EoT) Visit equivalent to the Week 24 assessments (except trial medication administration). Every effort should be made for all patients to return for a Safety Follow-up (SFU) Visit 10 weeks after last drug administration.
3. All efficacy (e.g., PASI, and sPGA) and safety assessments will be performed by blinded personnel.
4. A chest X-ray is to be taken at Screening. Alternatively, results from a chest X-ray taken within 12 weeks of Screening can be used.
5. Patients must have a negative tuberculosis (TB) screening assessment, including a purified protein derivative (PPD) skin test or interferon gamma-releasing assay (IGRA) (e.g., QuantiFERON[®] TB Gold or T-SPOT[®].TB). In addition, a TB test can be performed at any time during the trial if the investigator considers it clinically necessary.
6. Vital signs include measurement of body temperature, blood pressure, and pulse rate (all in the sitting position after a 5-minute rest).
7. Adverse events (AEs) will be collected from the time of informed consent. Adverse events continuing at the SFU Visit must be followed to resolution or followed up as agreed by the investigator and medical monitor. For patients who complete the trial or who discontinue the trial early, new AEs will be captured for up to 10 weeks after last drug administration (SFU Visit).
- 8.
9. Trial medication should be administered at Day 1, with the second injection 7 days later and subsequent injections every 2 weeks thereafter (\pm 2 days up to Week 14 and \pm 3 days from Week 16 onward).

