6.2.3 Follow-up Period and Trial Completion

Patients who discontinue the trial prematurely at any time after Day 1 including patients with discontinued treatment at week 16 due to lack of efficacy (but do not withdraw their consent) will, at discontinuation, have an End of Treatment (EoT) Visit equivalent to the Week 24 assessments (except trial medication administration). Patients who discontinue the trial will also be required to have all of the evaluations planned for Visit 10 (Week 34) 10 weeks after their last administered dose of trial medication. These patients should be registered as prematurely discontinued in IRT.

The following will be performed/collected:

- Urine pregnancy test for women of child-bearing potential
- Physical examination, including weight (kg) (see Section 5.3.1)
- Vital signs
- Laboratory testing (serum chemistry, hematology, and urinalysis)
- Previous and concomitant therapy (see Section 4.2)
- Assessment of AEs and concomitant therapy
- Review patient diary
- TB test

Unscheduled visit assessments

Patients may attend the trial site for unscheduled visits at any time for additional safety monitoring at the discretion of the investigator.

All abnormal values that are judged clinically relevant by the investigator will be monitored using the appropriate tests until a return to a medically acceptable level is achieved. Adverse

events persisting after trial completion must be monitored until they have normalized or have been sufficiently characterized.

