7.3.4 Safety analyses

Adverse events will be coded using the Medical Dictionary for Drug Regulatory Activities (MedDRA). The analysis of AEs will be based on the concept of treatment-emergent AEs. That means that all AEs with an onset between start of treatment and end of the REP, a period of 10 weeks after the last dose of trial medication, will be assigned to the treatment

period for evaluation. AEs that start before first drug intake and deteriorate under treatment will also be considered as ‘treatment-emergent’. Other AEs will be assigned to the appropriate trial phases, i.e., screening or post-treatment.

All treated patients will be included in the safety analysis. In general, safety analyses will be descriptive in nature and will be based on BI standards. No hypothesis testing is planned.

Statistical analysis and reporting of adverse events will concentrate on treatment-emergent adverse events. To this end, all adverse events occurring between start of treatment and end of the residual effect period will be considered ‘treatment-emergent’. The residual effect period is defined as 10 weeks after last dose of trial medication. Adverse events that start before first drug intake and deteriorate under treatment will also be considered as ‘treatment-emergent’.

Frequency, severity, and causal relationship of adverse events will be tabulated by system organ class and preferred term after coding according to the current version of the Medical Dictionary for Drug Regulatory Activities (MedDRA).

Laboratory data will be analysed both quantitatively as well as qualitatively. The latter will be done via comparison of laboratory data to their reference ranges. Values outside the reference range as well as values defined as clinically relevant will be highlighted in the listings. Treatment groups will be compared descriptively with regard to distribution parameters as well as with regard to frequency and percentage of patients with abnormal values or clinically relevant abnormal values.

Vital signs, physical examinations, or other safety-relevant data observed at screening, baseline, during the course of the trial and at the end-of-trial evaluation will be assessed with regard to possible changes compared to findings before start of treatment.

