16.1.1. ADVERSE EVENT SPECIFIC DERIVATION

16.1.1.1. Treatment Emergent Adverse Event

Treatment-Emergent Adverse Events (TEAEs) are defined as AEs that started or worsened on or after the first dose of trial medication and prior to the last date of trial medication + 10 weeks (70 days) inclusive.

There is one specific period of interest:

- Period 1 starts on the first administration day (Day 1 visit) and finishes prior to the visit date of Day 113 visit.

Period 1 Treatment-Emergent Adverse Events (P1 TEAEs) are defined as AEs that started or worsened on or after the first dose of trial medication during period 1 and prior to or at the last date of trial medication during period 1 + 10 weeks (70 days) inclusive.

Non-TEAEs will be classified as "Screening" if AE start date is strictly prior the first injection date. Non-TEAEs will

Document: \\ieedc-nas01a:\Boehringer_Ingelheim\BI_695501\XXA39605\Biostatistics\Documentation\SAP\15-v2.0\BI 1297.12 SAP v2.0 31JAN2018.docx

Author: Version Number: 2.0
Version Date: 31JAN2018

Template No: CS_TP_BS016 Revision 4
Effective Date: 01Apr2016

Reference: CS_WI_BS005

be classified as “Post treatment” if AE start date is strictly after the last injection date + 70 days.

See APPENDIX 2 for handling of partial dates for AEs. In the case where it is not possible to define an AE as treatment-emergent or not, the AE will be classified by the worst case, i.e., treatment-emergent in the period of the last injection of trial medication.

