16.1.6.6. Anaphylactic reactions

Anaphylactic reactions are those events recorded as MedDRA code in the pre-defined Standardized MedDRA Queries (SMQ) = “Anaphylactic reactions” (narrow)

Anaphylactic reaction adverse events of special interest (Anaphylactic reaction AESI) are those events both identified as Anaphylactic reactions and recorded as “Adverse Event of Special Interest” equal to “Yes” on the Adverse Events page of the eCRF.

Anaphylactic reactions will also be listed. The listing will include the “Adverse Event of Special Interest” equal to “Yes” information from the Adverse Events page of the eCRF as a flag.

Document: \\eedc-nas01a:\Boehringer_Ingelheim\BI_695501\XXA39605\Biostatistics\Documentation\SAP\15
-v2.0\BI 1297.12 SAP v2.0 31JAN2018.docx

Author: Version Number: 2.0
Version Date: 31JAN2018

Template No: CS_TP_BS016 Revision 4
Effective Date: 01Apr2016

Reference: CS_WI_BS005

16.1.7. AES OCCURRING AFTER THE LAST INJECTION FOR SUBJECTS DISCONTINUED DUE TO LACK OF EFFICACY

Subjects who discontinued treatment due to lack of efficacy will be identified from “End of treatment visit” eCRF page, where “Reason for End of Treatment” is “Lack of Efficacy”.

Number of subjects, percentages, and number of events occurring after the last injection and prior to the last injection + 10 weeks for subjects discontinued due to lack of efficacy by SOC and PT will be prepared.

AEs occurring after the last injection and prior to the last injection + 10 weeks for subjects discontinued due to lack of efficacy will be listed.

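### Protocol 5.3.6.2 narrows AE recording after early discontinuation to related SAEs and related AESIs, in conflict with Flow Chart footnote 7 and the 10-week treatment-emergent window

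*Protocol*

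**What the plan says.** Under the heading on AE collection, Protocol 5.3.6.2 lists what must be entered on the eCRF. From consent through the residual effect period (REP, 10 weeks after the last dose) this is "all AEs (serious and non-serious) and all AESIs". An exception follows, introduced by *However*. If a patient stops trial medication prematurely but stays in the trial, which the text explains as having further visits planned, then from that time until the patient's end of trial "the Investigator must report related SAEs and related AESIs". A little further on, the same section states: "All AEs which occurred through the treatment phase and throughout the REP will be considered as on treatment".

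Flow Chart footnote 7 covers patients who complete the trial and those "who discontinue the trial early, new AEs will be captured for up to 10 weeks after last drug administration (SFU Visit"). It sets no limit by seriousness or relatedness. Footnote 2 counts patients who miss PASI 50 at Week 16 among the early discontinuers. Protocol 6.2.3 gives all early discontinuers an End of Treatment visit and requires them to "have all of the evaluations planned for Visit 10 (Week 34) 10 weeks after their last administered dose of trial medication".

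The analysis rules have no exception for early stoppers:
- Protocol 7.3.4 assigns to the treatment period "all AEs with an onset between start of treatment and end of the REP".
- SAP 16.1.1.1 sets the end of the window as "prior to the last date of trial medication + 10 weeks (70 days) inclusive".
- SAP 16.1.7 plans a table and a listing, for patients stopped for lack of efficacy, of "events occurring after the last injection and prior to the last injection + 10 weeks".

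**The concern.** The exception starts when medication stops, not when the REP ends. For an early stopper, planned follow-up ends at about the same time as the REP, so the narrow rule covers nearly all of the post-stop period in which footnote 7 expects full capture.

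If sites apply it, three kinds of post-stop event need not reach the eCRF: non-serious AEs that are not AESIs, unrelated SAEs, and unrelated AESIs. The patients remain in the safety analysis set with a window that the analysis treats as fully observed. The outputs would be affected as follows:
- Overall AE, SAE, AESI and infection summaries would be undercounted.
- The SAP 16.1.7 output would shrink largely to related SAEs and AESIs, in exactly the group it was designed to describe.
- The secondary safety endpoint would miss patients whose first related AE is non-serious, not an AESI, and after the stop.
- Tables of related SAEs and of TEAEs leading to discontinuation would be essentially unaffected.

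**Working it through.** **Who falls under the exception.** The test in 5.3.6.2 is whether further visits are planned. Protocol 6.2.3 plans them for early discontinuers and names those stopped at Week 16 for lack of efficacy. Protocol 3.3.4.1 makes withdrawal from treatment the rule for that group, so the design itself creates it.

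**Does the exception narrow the rule?** The preceding item already requires all AEs and all AESIs. A further duty to report related SAEs and related AESIs adds nothing to it, so the contrasting sentence has a function only if it restricts. Reporting to the sponsor has its own later heading, so this sentence concerns eCRF collection.

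**The plan's own window.** 10 weeks × 7 = 70 days. The last planned dose is on Day 162 (SAP 13), and 162 + 70 = 232. This is the safety follow-up day in the Flow Chart, so the 70-day window reproduces.

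**Days under the narrow rule.** Dose and visit days are from the Flow Chart. The stop is taken to be decided at the efficacy visit, with dosing on schedule until then.

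Window end = last dose + 70. Gap = window end − stop visit. Share = gap ÷ window end.

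| Stop visit | Last dose | Visit day | Window end | Gap (days) | Share of window |
|---|---|---|---|---|---|
| Week 4 | 22 | 29 | 92 | 63 | 68% |
| Week 8 | 50 | 57 | 120 | 63 | 53% |
| Week 12 | 78 | 85 | 148 | 63 | 43% |
| Week 16 | 106 | 113 | 176 | 63 | 36% |
| Week 20 | 134 | 141 | 204 | 63 | 31% |

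In each row 63 of the 70 REP days (90%) fall under the narrow rule. With the ±3-day window on the Week 16 visit, the gap runs from 176 − 116 = 60 days (34%) to 176 − 110 = 66 days (38%).

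**Comparison with a continuing patient.** In the SAP Period 1 analysis, a patient who passes PASI 50 also has Day 106 as the last Period 1 dose and Day 176 as the window end, with 0 days lost. Period 1 tables would then pool fully and partly observed patients over the same nominal window.

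**Possible effect on the secondary endpoint.** The documents give no early-stopping rate and no post-stop event rate, so both are assumptions:
- Early stopping in 5% to 20% of 300 gives 15 to 60 patients.
- Suppose 2% to 10% of these have their first related, non-serious, non-AESI event after the stop. The loss is then 0.05 × 0.02 = 0.1 percentage points up to 0.20 × 0.10 = 2.0 percentage points.
- For any AE outside the narrow categories, an assumed 10% to 30% of early stoppers gives 15 × 0.10 = 1.5 up to 60 × 0.30 = 18 patients with an unrecorded event.

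**The case against.** The best defence has four parts.

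1. **Wording.** The sentence does not say that *only* related SAEs and AESIs are reported, whereas the next item, on the time after end of trial, does use that word. This is fair, but it leaves the contrasting sentence without a purpose.
2. **Population.** Footnote 2 and Protocol 6.2.3 describe these patients as discontinuing the trial, so the exception might be template text that applies to almost nobody. That reading is possible and shows that the terms are used loosely. By the section's own test of planned visits, however, these patients qualify.
3. **Missing figure.** The figure under the AE collection heading is not shown in the public document and may clarify the rule. This stands as a limit on certainty, although the text would still disagree with footnote 7.
4. **Evidence of full collection.** Protocol 6.2.3 lists AE assessment for early discontinuers, Protocol 5.3 has AEs assessed throughout, sites keep records of all AEs in patient files, and SAP 16.1.7 suggests that its authors expected the events to be in the database. This makes full capture plausible and recovery from source possible. It does not tell a site which instruction takes precedence for the eCRF.

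It is also right that Protocol 7.3.4 and the SAP sections classify or tabulate recorded events and do not instruct sites. The direct conflict is between the exception and footnote 7. The analysis windows are where the consequence appears. Finally, shares of days are not shares of events, and the percentage-point range rests wholly on assumed rates.

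**Conclusion.** The concern holds: the text is wrong as written. Protocol 5.3.6.2 and Flow Chart footnote 7 give incompatible collection rules for early stoppers, and the analysis assumes the fuller one. The firm figure is 63 days without full capture, which is 36% of the window for a Week 16 PASI 50 failure. The loss of 0.1 to 2.0 percentage points in the secondary safety endpoint is only illustrative.

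The undercount depends on sites having followed the exception, which the documents do not show. Safety is descriptive and the same rule applies in both arms, so a distorted comparison arises mainly if early stopping or post-stop event rates differ by arm. Nothing in the documents shows that. The sponsor should correct this, but it does not threaten the primary conclusion.

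**What to change.** In Protocol 5.3.6.2, delete the exception for patients who stop medication prematurely, or limit it to the time after the REP. All AEs are then collected for every treated patient who remains in follow-up through 10 weeks after the last dose, which agrees with footnote 7, Protocol 7.3.4, and SAP 16.1.1.1 and 16.1.7.

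The sponsor should also establish which rule sites applied. If any used the exception, footnote the affected AE tables and the SAP 16.1.7 output as incompletely captured after the stop.

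The protocol change is one sentence. The End of Treatment and safety follow-up visits with AE assessment are already scheduled for these patients, so the added burden is a little more data entry. Checking site practice takes some further effort.

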5.7 APPROPRIATENESS OF MEASUREMENTS

All measurements performed during this trial are standard measurements in psoriasis treatment trials and will be performed in order to monitor safety aspects or assess treatment response in an appropriate way.

Therefore, the appropriateness of all measurements applied in this trial is assured.

Information about race should be obtained from all study participants as allowed by local regulations. This is because the prevalence and characteristics of psoriasis differ widely between patients of different racial origin. It will thus be worthwhile to assess if patients of different race will respond differently to the study treatment.

6. INVESTIGATIONAL PLAN

6.1 VISIT SCHEDULE

A schedule of assessments is provided in the [Flow Chart](#).

Each visit date (with its window) is to be counted from Day 1 (randomization). If any visit has to be rescheduled, the 2-week regimen for trial medication administration should resume from the time the last dose was administered. Additional visits for the purpose of re-testing of laboratory parameters or AE monitoring may be included as deemed necessary by the investigator.

- A visit window of -1 / + 2 days is permitted for Visit 2 (Day 1)
- A visit window of ± 2 days is permitted from Visit 3 up to Visit 7
- A visit window of ± 3 days is permitted for Visit 8 to Visit 10

All assessments should be performed prior to administration trial medication, unless otherwise specified. Laboratory samples must be drawn prior to trial medication injection.

The questionnaire will be completed at the site by the patient (DLQI) before any investigations or discussions about their disease with the clinic staff and may only be recorded by a trial nurse/investigator on behalf of the patient if the patient has difficulty writing during the visit or is unable to read. This must be documented clearly in the patient notes.

Also the scales are to be completed by study site personnel (PASI sPGA,

All questionnaires and scales are detailed in Appendix 10.

The total estimated volume of blood that will be drawn from each patient during the course of the trial is shown in [Table 6.1: 1](#).

Table 6.1: 1 Estimated blood sample volumes per patient

Parameter	Sample volume (mL)	Number of samples	Total volume (mL)
Laboratory tests (including serum chemistry, serum pregnancy test)	3	6	18
Hematology	3	6	18
Infection screen	4	1	4
TB test	3	2	6
Approximate total			82

Abbreviations: ADA=anti-drug antibodies; nAb=neutralizing ADA; TB=tuberculosis.

Additional samples may be required if medically indicated, e.g., at unscheduled visits to follow safety findings.

